**Fig. 3 Workflow for 2D antiscatter grid installation in the CBCT System**

[figure not shown]
1. Components of the CBCT system. 2D antiscatter grid will be installed on the x-ray detector on the right. Detector is underneath the gray protective cover.

2. Once the protective cover is removed, the detector and the standard antiscatter grid (white plate, surrounded by red line) on the detector are accessible. Grid is fixed on the detector with 8 screws (blue arrows). For the research CBCT scan, this grid will be removed by taking the screws out.

3. The sideview of the detector and the standard antiscatter grid.

4. After removing the standard grid, the 2D grid will be installed on the detector.

### **An overview of the 2D grid installation and research CBCT scan process:**

1. (See Figure 3). Before the research CBCT scan, the study team will remove the protective cover on the kV x-ray detector and uninstall the standard grid on the detector by removing the screws.
2. They will install the 2D grid on the detector, and a protective cover (as in Picture 1) will be installed over the 2D grid.
3. The process in Steps 1 and 2 will take less than 10 minutes.
4. Subsequently, the study participant will be positioned on the CBCT scanning couch as in his/her radiation treatment position.
5. Study team will leave the room and prepare the standard clinical CBCT scanning protocol that is used for the participant's standard clinical CBCT scans. This way, we will ensure that the same scanning technical parameters will be used for the research and the standard clinical CBCT scan. They will initiate the research CBCT scan. The scan itself will take 1 minute or less. The process in step 5 is expected to take less than 5 minutes.
6. Study team will go back into the room and take the study participant out of the room.
7. After departure of the participant, the study team will acquire one more CBCT scan without the participant. This "blank" scan will be used for system calibration purposes.
8. Study team will download all the CBCT scan raw data of the participant and the calibration scan. They will do the CBCT image reconstruction by using the raw data. This step does not need to be completed immediately. It can be performed hours or days after the research CBCT scan.
9. Study team will uninstall the 2D grid and reinstall the standard grid on the detector. They will perform the calibrations needed to bring the system back to its standard clinical stage. The calibrations performed at this step are part of the standard operating procedures, and they are provided by the CBCT system vendor (e.g. Varian Medical Systems).

It is important to emphasize that research scans described above will not be used during the treatment of the study participant or making clinical decisions. These research CBCT scans will be used solely for research purposes.

## **6.2 PREPARATION/HANDLING/STORAGE/ACCOUNTABILITY**

### **6.2.1 ACQUISITION AND ACCOUNTABILITY**

2D antiscatter grid prototypes will be fabricated by a metal 3D printing manufacturer and will be assembled by PI's team at University Colorado Anschutz Medical Campus. These prototypes will be used throughout the study in all participating institutions. Study investigators will oversee the storage, installation and use of the grid prototypes during research CBCT scans.

## **6.2.2 FORMULATION, APPEARANCE, PACKAGING, AND LABELING**

The 2D grid prototypes will be fabricated from pure tungsten and assembled together using aluminum components. 2D grid will be fabricated using Powder Bed Laser Melting or Direct Metal Laser Sintering additive manufacturing processes. They will be up to 43 cm in width, up to 43 cm in length, and up to 3 cm in height covered with a carbon-fiber or equivalent enclosure.

While the manufacturing process for the 2D grid is different from standard radiographic grids, such as the one used in Varian TrueBeam, materials used in the radiographic grid are similar to the materials in the 2D grid assembly; radiographic grid is composed of lead lamellae separated by fiber spacers. A carbon-fiber or equivalent enclosure is placed around the grid structure.

## **6.2.3 PRODUCT STORAGE AND STABILITY**

2D grid prototypes will be placed in an enclosure while being stored in the locked storage cabinet and during transport from storage to the linac vault to prevent accidental damage to the grids. Grids are kept at room temperature, and they are expected to retain their properties for at least 5 years. The 2D grid and its enclosure do not change form due to x-ray irradiation during CBCT scans.

## **6.2.4 PREPARATION**

Once it is assembled, the 2D grid does not require any preparation for each research CBCT scan.

## **6.3 MEASURES TO MINIMIZE BIAS: RANDOMIZATION AND BLINDING**

Randomization or blinding is not needed during acquisition of CBCT scans of the participants.

In the primary analysis, regions of interest (ROIs) will be placed in CBCT scans by the study team. These regions of interest will be used for calculation of objective image quality metrics. To prevent bias in ROI placement, all CBCT and CT images of a given participant will be coregistered first, such that anatomical locations of ROIs will be comparable in coregistered image sets. Moreover, the locations of ROIs will be cross-checked by a second team member.

## **6.4 STUDY INTERVENTION COMPLIANCE**

- The same immobilization devices, patient position, and scanning protocol will be used for both research and standard clinical CBCT scans. A checklist will be used to assure that the imaging protocol parameters are the same for both research and standard clinical CBCT scans.

- Excessive patient motion during a CBCT scan may degrade image quality and bias the study. The effects of patient motion will be evaluated on a case-by-case basis by the PI. If image quality degradation due to patient motion is deemed excessive, the CBCT scan will be excluded from the study.

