### 3 OBJECTIVES AND ENDPOINTS

OBJECTIVES	ENDPOINTS	JUSTIFICATION FOR ENDPOINTS
Primary: To assess the improvement in tissue visualization in CBCT images	Improvement in image quality and quantitative accuracy as measured by established objective image quality metrics.	We will evaluate absolute CT number error, image artifact amplitude, and contrast to noise ratio, which are metrics that quantify the image quality. We hypothesize that values of these metrics will be improved in CBCT images acquired with the 2D grid.
Secondary: To evaluate the accuracy of tissue delineation in CBCT images by auto-segmentation software.	Similarity of anatomical structures delineated by auto-segmentation software and expert observers, as measured by established similarity metrics.	Auto-segmentation software is a highly desired tool that is expected to generate delineations similar to delineations by human observers. We will use delineations by observers as the gold standard. We will measure the similarity between the auto-segmented delineations and observer delineations.
Tertiary/exploratory: To assess the utility of CBCT images in qualitative and quantitative imaging tasks	Improvement in qualitative and quantitative imaging tasks as measured by quality metrics pertinent to each task	CBCT images are used in a wide variety of tasks. Some task examples are tissue delineation for treatment adaptations, radiomics feature evaluation, radiotherapy dose calculations, and target localization. Thus, image quality metrics will be identified for each task, and the utility of CBCT images in each task will be evaluated using the quality metrics associated with each task.

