## 9.3 POPULATION FOR ANALYSES

Data from participants who complete both research and standard clinical CBCT scans, and the scans are evaluable, will be used for primary and secondary analyses. The study intervention is a CBCT scan for observation purposes, without any anticipated adverse effects on the participant. Therefore, safety analysis dataset is not needed in this study.

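### Motion exclusions are judged on image quality, the primary endpoint, with no masking, pre-set criterion or timing rule, so one-sided exclusion could bias the paired comparison

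*Combined protocol and SAP*

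**What the plan says.** The exclusion rule is in Section 6.4: "The effects of patient motion will be evaluated on a case-by-case basis by the PI", and then "If image quality degradation due to patient motion is deemed excessive, the CBCT scan will be excluded from the study". No threshold, grading scale, masked reader or timing is given.

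Section 9.3 defines the set for the primary and secondary analyses as "Data from participants who complete both research and standard clinical CBCT scans, and the scans are evaluable". It does not define evaluable.

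Section 3 gives the primary endpoint as "Improvement in image quality and quantitative accuracy as measured by established objective image quality metrics". The metrics are absolute CT number error, artifact amplitude and contrast-to-noise ratio. Section 9.4.2 compares them within patient in a linear mixed model on the log scale, and plans no analysis that restores excluded scans.

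On bias control, Section 6.3 says "Randomization or blinding is not needed during acquisition of CBCT scans of the participants". For the primary analysis "regions of interest (ROIs) will be placed in CBCT scans by the study team", with two safeguards: "To prevent bias in ROI placement, all CBCT and CT images of a given participant will be coregistered first", and "the locations of ROIs will be cross-checked by a second team member". Blinded reading appears only in the exploratory observer studies (Sections 9.4.1 and 9.4.7).

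**The concern.** Motion is recognised by its effect on the image, and image quality is what the trial measures. Whoever decides that a scan is too degraded is therefore making a judgement close to the outcome. If that person knows the scan type, or has seen the metrics, a poor grid scan may be set aside more readily than an equally poor control scan, or the reverse. Because the whole pair goes, a few such decisions shift the mean paired difference and also shrink its standard deviation.

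Section 9.4.1 draws its conclusion from statistical significance, so the false-positive rate matters even in a pilot. As planned, the report would contain nothing from which a reader could tell whether exclusions had been even-handed.

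**Working it through.** The plan gives no figure for exclusions or their effect. The only sample-size calculation (Section 9.2) concerns the ICC, now an exploratory measure, and does not bear on this point.

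**Inputs from the documents**
- 32 photon pairs (Groups 1–3) and 10 proton pairs (Group 4): Sections 4.1 and 9.2.
- The two cohorts are analysed separately: Section 9.4.1.
- Mixed model with a random patient effect on log metrics: Section 9.4.2.

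**Assumptions.** The documents give no standard deviation, within-patient correlation or expected exclusion rate. I take normal log metrics, correlation ρ from 0.3 to 0.8, and 2 or 3 exclusions of 32, or 1 of 10.

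**Model with no true effect.** For patient i, with higher values meaning better quality, the grid scan is G = b + e and the control scan is C = b + f, where Var(b) = ρ and Var(e) = Var(f) = 1 − ρ. The paired difference is d = G − C. After dropping q of n pairs, m = n − q remain and T = mean(d) / (s_d / √m). A false win for the grid is T above the 97.5% point of t with m − 1 degrees of freedom; for example, 32 − 2 = 30 pairs gives 29 degrees of freedom. The paired t-test stands in for the mixed model. The standard deviation cancels from T, so the rates do not depend on it.

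**Simulated chance of a false win for the grid, for one metric** (repeat runs differ by a few tenths of a percentage point)

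| Which pairs are dropped | 2 of 32 | 3 of 32 | 1 of 10 |
|---|---|---|---|
| None (nominal) | 2.5% | 2.5% | 2.5% |
| Those where either scan is poorest, same rule for both | about 2.5% | about 2.5% | about 2.5% |
| Those with the poorest grid scan, ρ = 0.5 | 5.7% | 7.3% | 4.6% |
| The same, ρ from 0.8 down to 0.3 | 4.2–6.4% | 5.0–8.7% | 3.5–5.0% |
| Those with the paired difference least favourable to the grid (extreme) | about 13% | about 21% | about 9% |

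A higher ρ gives less inflation: a poor grid scan then mostly reflects a difficult patient, whose control scan is poor too.

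**Threshold version, n = 32, ρ = 0.5.** Dropping only grid scans in the lowest 5%, 10% or 15% of quality gives 4.7%, 7.5% and 10.7%. Applying the same threshold to both scan types gives 2.4–2.5%, with about 29, 27 and 24 pairs left. Unequal exclusion causes the inflation; exclusion as such does not.

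**Replacement.** Section 1.1 allows up to 50 enrolled against a minimum of 42, a margin of 50 − 42 = 8, partly for non-evaluable patients. Replacing lost pairs does not protect: enrolling 34 and dropping the 2 least favourable gives 12.4%.

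**The case against.** The rule is narrower than exclusion for poor image quality. Its ground is degradation from patient motion; shading, CT number error or low contrast produced by the grid would not qualify. Section 5.2 already screens out patients who cannot lie still or whose earlier scans show excessive artifacts, and Section 6.4 requires the same immobilisation, position and protocol for both scans. Exclusions may be few, and could as easily remove poor control scans. All of this stands. It limits the likely size of the problem but does not make the decision even-handed or checkable.

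The extreme row of the table models someone ranking paired differences, which Section 6.4 does not describe. That also stands, so the grid-scan rows are the better guide.

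Three stronger readings are tempting and not supported:
- **That the PI knows the scan type and will favour the grid.** The documents never say that the PI is unmasked. They plan no masking, and the PI's team assembles the grids and the study team reconstructs the research scans (Section 6.1.1), so knowledge is a fair inference. Intent or direction is not.
- **That region-of-interest placement favours the grid.** Section 6.3 provides coregistration and a second-person cross-check, and Section 9.4.1 ties each region to the simulation CT. These do not mask the choice of location, but no direction of bias follows.
- **That scan order favours the grid.** Section 1.3 leaves order free, and Section 9.4.2 names no order term. The documents give no mechanism, direction or size for an order effect. In the photon cohort the control scan also guides treatment, so order is partly set by care.

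**Conclusion.** The concern holds for the motion exclusion rule: it acts on a judgement close to the endpoint, with no masking planned, no criterion and no fixed timing, and its effect goes untested. Bias is possible, not shown, and needs one-sided exclusion. If it occurred, a handful of exclusions would roughly double or triple the 2.5% false-win rate: about 4–6% for 2 of 32, 5–9% for 3 of 32 and 3.5–5% for 1 of 10, with about 13%, 21% and 9% as the extreme. These figures rest on the assumed correlation of 0.3–0.8, normal log metrics and the chosen numbers of exclusions. They describe a single metric. The change is worth making because it is cheap and an even-handed rule removes the inflation. No bias towards the device is claimed from region placement or scan order.

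**What to change.** In Sections 6.4 and 9.3:
1. State one written motion criterion in advance, and apply it to both scans of every pair.
2. Have motion judged on images with scan type removed, and lock the decision before any metric is computed. Name the reader; the documents assign nobody to a masked motion review.
3. Define evaluable by reference to that criterion, and report the number of exclusions and reasons by scan type and cohort.
4. Add an analysis of all acquired pairs alongside the primary one.

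Minor additions in Sections 6.3 and 9.4.2: use the same coregistered region on both CBCTs of a participant, making any adjustment for anatomical change to both; and record scan order.

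The cost is protocol wording and some reader time, with no extra scans or participants. There are two downsides. Grid images may be partly recognisable without their labels, so masking may be incomplete; the all-pairs analysis is the safeguard in that case. That analysis will also be noisier, because it keeps motion-affected scans.

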## **6.5 PROHIBITED THERAPY**

There are not any prohibited therapies.

## **6.6 CONCOMITANT THERAPY**

There are not any concomitant therapies within this study.

# **7 STUDY INTERVENTION DISCONTINUATION AND PARTICIPANT DISCONTINUATION/WITHDRAWAL**

## **7.1 DISCONTINUATION OF STUDY INTERVENTION (STOPPING RULES)**

The Sponsor-Investigator has the right to terminate this study at any time. Reasons for terminating the study may include, but are not limited to, the following:

- The incidence or severity of adverse events in this or other studies indicates a potential health hazard to patients.
- Patient enrollment is unsatisfactory.

## **7.2 PARTICIPANT DISCONTINUATION/WITHDRAWAL FROM STUDY**

Participants are free to withdraw from participation in the study at any time upon request.

In addition, the investigator has the right to withdraw a patient from the study at any time. Reasons for withdrawal from the study may include, but are not limited to, the following:

- Patient withdrawal of consent at any time
- Any medical condition that the Sponsor-Investigator determines may jeopardize the patient's safety if he or she continues in the study
- Sponsor-Investigator determines it is in the best interest of the patient
- Patient non-compliance with study procedures

Participants must discontinue study intervention if they experience any of the following:

- Any medical condition that may jeopardize patient safety.

Every effort should be made to obtain information on patients who withdraw from the study. The primary reason for withdrawal from the study should be documented on the appropriate eCRF.

## **8 STUDY ASSESSMENTS AND PROCEDURES**

### **8.1 EFFICACY ASSESSMENTS**

The main hypothesis of the study is that 2D antiscatter grid improves tissue visualization and quantitative accuracy in CBCT images. An image quality evaluation study will be performed (described in Section 9). Values of objective image quality metrics extracted from CBCT images will be used to assess tissue visualization.

The efficacy of tissue visualization improvement in research CBCT scans will be assessed with respect to standard clinical CBCT scans.

The efficacy analyses for the secondary objective will be conducted in a similar fashion, and efficacy of study intervention will be assessed with respect to standard clinical CBCT scans.

For the tertiary objective, multiple evaluations will be performed to assess the utility and efficacy of research CBCT scans in different clinical tasks. As this is a pilot study, the PI will determine which clinical tasks will likely benefit from the research CBCT scans acquired in this clinical trial. Some examples of such clinical tasks are: 1) It is hypothesized that clinicians can more consistently delineate anatomy in CBCT images acquired with the 2D grid. An observer study will be conducted to evaluate tissue visualization performance in CBCT images. 2) The consistency of radiomics features in research and standard clinical CBCT scans will be measured and evaluated by using MDCT images of participants as reference, as described in Section 9. MDCT scans will be acquired as part of the standard clinical care of participants. 3) Image quality for target localization tasks will be assessed in a subjective image quality evaluation study, where observers will rank the quality of CBCT images. 4) Image quality will be assessed using objective image quality metrics, such as noise, contrast, contrast to noise ratio, and CT number uniformity. 5) CBCT-based dose calculation accuracy by generating treatment plans using CBCT images, and errors in dose volume histogram metrics will be assessed with respect to reference dose in MDCT-based treatment plans. To reiterate, these are example assessments in this exploratory objective, and the PI will determine the specific CBCT-based clinical tasks to be assessed.

## 8.2 SAFETY AND OTHER ASSESSMENTS

The intervention of this study (one research CBCT scan for photon therapy cohort, and two research CBCT scans for the proton therapy cohort) is not expected to have any detectable effects on study participants, as described in Section 2.3.1. Therefore, evaluation of the participant, such as physical examination or specimen collection and analysis, will not be performed as part of this study.

## 8.3 ADVERSE EVENTS

### 8.3.1 DEFINITION OF ADVERSE EVENTS (AE)

**Adverse event** means any untoward medical occurrence associated with the use of an intervention in humans.

Because this is an imaging study, where no clinical decision will be altered, only AEs that are related to the research intervention or the use of the device will be recorded. The only research procedure is a CBCT scan with the 2D grid attached. In the proton therapy cohort, one more CBCT scan will be acquired without the 2D grid.

As described in Sec. 2.3, we do not anticipate adverse events due to the research intervention itself, such as acute skin reaction due to CBCT imaging dose. However, unforeseen incidents, such as breakdown of the grid during the scan, may occur. Such incidents will be recorded as an AE.

### 8.3.2 DEFINITION OF UNANTICIPATED ADVERSE DEVICE EFFECTS (UADE)

**Unanticipated Adverse Device Effect (UADE)** is any serious adverse effect on health or safety or any life-threatening problem or death caused by, or associated with, a device, if that effect, problem, or death, was not previously identified in a nature, severity, or degree of incidence in the investigational plan or application (including a supplementary plan or application), or any other unanticipated serious problem associated with a device that relates to the rights, safety, or welfare of subjects (21 CFR 812.3(s)). This includes any adverse event resulting from insufficiencies or inadequacies in the instructions for use, the deployment, the implantation, the installation, the operation, or any malfunction of the investigational medical device. Additionally, this includes any event that is a result of a use error or intentional misuse.

---

### 8.3.3 CLASSIFICATION OF AN ADVERSE EVENT

---

#### 8.3.3.1 SEVERITY OF EVENT

For AEs not included in the protocol-defined grading system, the following guidelines will be used to describe severity.

- **Mild** – Events require minimal or no treatment and do not interfere with the participant's daily activities.
- **Moderate** – Events result in a low level of inconvenience or concern with the therapeutic measures. Moderate events may cause some interference with functioning.
- **Severe** – Events interrupt a participant's usual daily activity and may require systemic drug therapy or other treatment. Severe events are usually potentially life-threatening or incapacitating.

---

#### 8.3.3.2 EXPECTEDNESS

Expectedness will only be documented for UADEs. The radiation oncologist will be responsible for determining whether a UADE is expected or unexpected. A UADE will be considered unexpected if the nature, severity, or frequency of the event is not consistent with the risk information previously described for the device.

---

### 8.3.4 TIME PERIOD AND FREQUENCY FOR EVENT ASSESSMENT AND FOLLOW-UP

The occurrence of an AE or UADE may come to the attention of study personnel during study visits and interviews of a study participant presenting for medical care, or upon review by a study monitor. All AEs including local and systemic reactions not meeting the criteria for UADEs will be captured on the appropriate CRF. Information to be collected includes event description, time of onset, clinician's assessment of severity, relationship to study product (assessed only by those with the training and authority to make a diagnosis), and time of resolution/stabilization of the event. All AEs related to the study intervention must be documented. All related AEs will be followed to adequate resolution.

Any medical condition that is present at the time that the participant is screened will be considered as baseline and not reported as an AE. UAPs will be recorded in the data collection system throughout the study.

Changes in the severity of an AE will be documented to allow an assessment of the duration of the event at each level of severity to be performed. AEs characterized as intermittent require documentation of onset and duration of each episode.

The PI will record all reportable events with start dates occurring any time after the start of the intervention until the completion of study visit #2. UADEs will be followed until resolution or stabilization. At each study visit, the investigator will inquire about the occurrence of AE/UADEs since the last visit.

---

